Detailed study procedures at each visit are listed below:

VISIT 1

The Subjects must present to Visit 1 wearing habitual contact lens or if not a contact lens wearer their spectacles (if applicable). If the subject is a habitual contact lens wearer and does not have their contact lenses they must be rescheduled.

Subjects will also will be requested to bring any distance/reading spectacles, package of their CLs, lens care solution, and rewetting/lubrication eye drops to the appointment, if not they must be rescheduled.

Visit 1: Screening			
Step	Procedure	Details	
1.1	Statement of Informed Consent	Each participant must read, understand, and sign the Statement of Informed Consent before being enrolled into the study. The Principal Investigator or his/her designee conducting the informed consent discussion must also sign the consent form. Note: The participant must be provided a signed copy of this document.	
1.2	Demographics	Record the participant’s date of birth, sex, race and ethnicity.	
1.3	Medical History and Concomitant Medications	Questions regarding the Subjects’ medical history and concomitant medications.	
1.4	Presbyopic Symptom Questionnaire	Confirm the subject is either already wearing a presbyopic correction (e.g., reading spectacles over contact lenses, or multifocal spectacles, etc.) or responds positively to at least one symptom on the “Presbyopic Symptoms Questionnaire.	
1.5	Habitual Visual Correction	Questions regarding the participant’s habitual lens/correction type and parameters. All Subjects will be asked about their previous CL wear including history of MF CL wear	
Interview (Pre-fit)			
1.6	CL Wear History, Occupation Hobbies, Visual Demands, Contact lens Success, Reasons for Success / Failure	Questions regarding the participant’s: 
 • Habitual correction • Occupation and hobbies • Visual demands, eg laptop, shift work, night driving, etc. • Success criteria with multifocal contact lenses • Factors affecting success/failure with multifocal contact lenses 	

1.7	Screening Eligibility	
All responses to Screening Inclusion Criteria questions must be answered “yes” and all responses to Exclusion Criteria must be answered “no” for the subject to be considered eligible.
 
If subject is deemed to be ineligible after screening, proceed to Final Evaluation and complete Subject Disposition. Refraction and Biomicroscopy forms are not required.
	
-----	-----------------------	--	--

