Visit 1: Baseline			
Step	Procedure	Details	
1.8	Entrance Distance VA (spectacles) if applicable	
Record distance logMAR high contrast VA with the participant’s spectacles (if applicable): OD, OS, OU.
 
Note: The acuity will be recorded to the nearest letter OD, OS, and OU.
	
1.9	Ocular Symptoms	Subjects will respond to a verbal open-ended symptoms questionnaire.	
1.10	Quest-Quant Questionnaire	The subject will respond to the Quest-Quant Questionnaire.	
1.11	PRO (CLUE) Questionnaire (if applicable)	If Subjects are habitual contact lens wearers they will complete the PRO (CLUE) Contact Lens performance questionnaires.	
1.12	Auto-refraction & Keratometry	Record auto refraction and Keratometry results.	
1.13	Subjective Sphero-Cylindrical Refraction	
Conduct balanced subjective Best Sphero-cylindrical Refraction.
 
Record the refraction and distance logMAR visual acuity to the nearest letter.
 
Note: Best distance monocular visual acuity with sphero-cylindrical refraction must be at least +0.20 logMAR and binocular visual acuity of at least +0.10 logMAR with refraction for the subject to enroll in the study.
	
1.14	Near Add Determination	The near reading addition will be determined using the binocular crossed cylinder technique at 40 cm followed by optimization in a trial frame in step 1.20 below.	
1.15	Ocular Dominance	Determine ocular dominance	

1.16	ADD Refinement	Place the BCC result in the trial frame and refine the near prescription with trial lenses (or flippers) under binocular conditions.	
1.17	Near Visual Acuity	Measure Near logMAR at 40cm with near prescription in a trial frame. Record the near visual acuity OD, OS and OU.	
1.18	Unilateral Cover Test	Record presence/absence of strabismus in each eye (OD, OS) at distance with the Sph-cyl Refraction in Trial Frame. Then record presence/absence of strabismus in each eye (OD, OS) at near (40 cm) with the Sph-cyl Refraction and Near Add in Trial Frame.	
1.19	Biomicroscopy	Non-dilated Slit Lamp Biomicroscopy will be performed. If the clearance of the fluorescein needs to be expedited, preservative-free rewetting drops or saline may be instilled.	

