1.20	Eligibility	All responses to corresponding Screening Inclusion Criteria questions must be answered “yes” and all responses to corresponding Exclusion Criteria must be answered “no” for the participant to be considered eligible. If participant is deemed to be ineligible after baseline, proceed to Final Evaluation and complete Subject Disposition. Biomicroscopy and Sph-cyl Refraction forms are not required.	
1.21	Near Stereo-acuity (40 cm)	Record Stereo-acuity at 40 cm using Near Stereo-Acuity test with the Sph-cyl Refraction and Near Add in Trial Frame.	
1.22	Fixation Disparity	Record distance fixation disparity with the Sph-cyl Refraction in place. Then record near (40 cm) fixation disparity with the Sph-cyl Refraction and Near Add in Trial Frame.	
1.23	Contrast Threshold	Record distance contrast threshold with the Sph-cyl Refraction in a trial frame: OD, OS and OU.	
1.24	Tear Break-Up Time (bare eye)	Measure and record (NITBUT) OD & OS with Placido disc topographer projecting onto tear film.	
1.25	Objective Accommodation	Record objective accommodation using WAM 5500 refractometer for 4m, 1m, and 40cm targets with the distance Sph-cyl Refraction OD & OS in	

		Trial Frame. Record the average measurement for each distance OD, OS.	
1.26	COAS (bare eye)	Measure the ocular aberrations using COAS 2 secs after blink, OD & OS @ distance target Coma over bare OD, OS.	
1.27	Topographer (bare eye)	Baseline imaging for lens centration using Medmont Topographer, over bare eye: OD, OS	
1.28	Exit distance VA	Record distance logMAR HCVA with the participant's spectacles (if applicable): OD, OS, OU.	
1.29	Schedule Follow-up	The subject will be scheduled to return for their next appointment in 1 to 14 days.	

VISIT 2

The Subjects must present to Visit 2 wearing spectacles (if applicable), not having worn any contact lenses (if applicable) on the day of the visit. If the subject is wearing or has worn their lenses the day of the visit they must be rescheduled.

Visit 2: Baseline Treatment 1			
Step	Procedure	Details	
2.1.	Adverse Events and Concomitant Medications Review	Record any changes in concomitant medications and any adverse events that may have occurred since the last scheduled study visit.	
2.2.	Non-Contact Lens Wear Compliance	Confirm the Subject has not worn contact lenses prior to the visit.	

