2.3.	Subject Reported Ocular Symptoms	If the participant reports ocular symptoms with their lenses, they will be recorded in the Subject Reported Ocular Symptoms eCRF	
2.4.	Personality test: BIG5	Have the subject conduct the personality test and record the subject's score.	
2.5.	Entrance Distance VA (spectacles) if applicable	Record distance logMAR high contrast VA with the participant's spectacles (if applicable): OD, OS, OU.	
2.6.	Blur Tolerance	Record the 1-meter distance binocular blur tolerance with intermediate (1m) refraction.	
2.7.	Pupil size	Measure and record pupil size in photopic & scotopic lighting using Pupilometer. Measure OD and OS at distance, intermediate(1m) and near (40cm).	
2.8.	Biomicroscopy	Non-dilated Slit Lamp Biomicroscopy will be performed.	

		If the clearance of the fluorescein needs to be expedited, preservative-free rewetting drops or saline may be instilled.	
2.9.	Continuance	Confirm the participant meets the criteria to continue.	

Visit 2: Treatment 1 Lens Fitting			
Step	Procedure	Details	
2.10.	Lens Selection	Select the lens distance spherical equivalent power and ADD based upon the fitting guide. Record the test lens parameters (power and lot number). Place the lenses on their eyes. Note: If a participant requires a study lens power that is not available, either as the initial selection or during a modification, they will be discontinued from the study. Complete the exit slit-lamp and VA and Final Evaluation. Sph-cyl Refraction form is not required.	
2.11.	Lens Insertion	Subjects or Investigator will insert the lenses. If the lens is uncomfortable, inspect for damage and remove, reinsert or replace as necessary. Damaged lenses will be stored in labeled vial with sterile saline, and clearly differentiated from the other worn lenses that will be shipped back to the Sponsor. Complete the Quality Product Complaint form.	
2.12.	Lens Settling	Allow the lenses to settle for at least 10 minutes.	
2.13.	Determine Visual Satisfaction	Determine if the participant's vision is acceptable with the lenses. Allow the participant to look down a hallway or out of a window for distance vision assessments, and for them to read a book, magazine or similar for near vision.	
2.14.	logMAR HCVA Acuity	Record distance and near (40cm) logMAR HCVA with study CLs: OD, OS, OU to the nearest letter	

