3.9.	Lens Fit Assessment:	Evaluate and grade lens centration, primary gaze movement, upgaze movement and tightness (push-up test). The participant should not proceed to wear the lenses if any of the following is observed: 
 • presence of limbal exposure (appearance of clear cornea) in any gaze • presence of edge lift • presence of unacceptable movement (excessive or insufficient) in all three movement categories (primary gaze, upgaze, and push-up). 
If either lens is deemed unacceptable, the participant will be discontinued from the study.
	

Visit 3: Treatment 1 Follow-up 1			
Step	Procedure	Details	
		Remove the lenses, perform a slit-lamp evaluation, and complete the Final Evaluation form.	
3.10.	Collection of unworn lenses (if applicable)	Collect unworn lenses returned by the subject when lens power has been optimized Note: If lens power was not changed allow the subject to use the unworn lenses dispensed at Visit 2 and dispense enough lenses of the same power to last the subject until their next visit.	
3.11.	Lens Removal	Remove and discard the lenses.	
3.12.	Biomicroscopy	Non-dilated Slit Lamp Biomicroscopy will be performed. If the clearance of the fluorescein needs to be expedited, preservative-free rewetting drops or saline may be instilled.	
3.13.	Insertion of Study Lenses	Dispense the participant new lenses that match the original distance and ADD power of the lenses that were removed in Step 3.11 above.	
3.14.	Post-Fit PRO (MRD) Questionnaire	Subjects will complete the PRO (MRD) Contact Lens performance questionnaires.	
3.15.	Stereo-Acuity: Near (40 cm) with CLs	Record Stereo-acuity using Near Stereo-Acuity test with CLs.	
3.16.	Contrast Threshold (CLs)	Record distance contrast threshold with CLs: OD, OS and OU with the study contact lenses	
3.17.	Pre-lens NITBUT	Measure and record NITBUT with Placido disc topographer projecting onto pre-lens tear film. OD, OS.	
3.18.	Objective accommodation (CLs)	Record objective accommodation using WAM 5500 refractometer for 4m, 1m, and 40cm targets with the CLs. OD, OS. Record the average for each distance measurement OD, OS.	
3.19.	COAS (over the CLs)	Measure the ocular aberrations using COAS, 2 secs after blink, OD & OS @ distance target Coma over the Contact lenses.	
3.20.	Topographer (lens centration)	Imaging for lens centration using Medmont Topographer, over CLs: OD, OS	

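### Tear break-up time, aberrations and lens centration are measured after fluorescein at Visits 1 and 3, and at Visit 3 on newly inserted lenses with no required settling time, so these secondary predictors may carry avoidable error

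*Combined protocol and SAP*

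**What the plan says.** All steps are in Section 7.2 of the combined protocol and SAP. NITBUT is non-invasive tear break-up time; COAS is the wavefront aberrometer; Medmont is the topographer.

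**Visit 1.** Biomicroscopy is step 1.19. Its text presumes dye: "If the clearance of the fluorescein needs to be expedited, preservative-free rewetting drops or saline may be instilled". Five steps later comes bare-eye NITBUT: "Measure and record (NITBUT) OD & OS with Placido disc topographer projecting onto tear film". Then come COAS (1.26), "Measure the ocular aberrations using COAS 2 secs after blink, OD & OS @ distance target Coma over bare OD, OS", and topography (1.27), "Baseline imaging for lens centration using Medmont Topographer, over bare eye: OD, OS". On arrival, "The Subjects must present to Visit 1 wearing habitual contact lens or if not a contact lens wearer their spectacles (if applicable").

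**Visit 2.** No contact lenses may have been worn that day. Pupil size is step 2.7 and biomicroscopy 2.8. After fitting, step 2.12 says "Allow the lenses to settle for at least 10 minutes".

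**Visit 3.** Lenses come out (3.11), biomicroscopy follows (3.12), and then step 3.13: "Dispense the participant new lenses that match the original distance and ADD power of the lenses that were removed in Step 3.11". A questionnaire (3.14), stereo-acuity (3.15), contrast threshold (3.16), NITBUT (3.17), accommodation (3.18) and COAS (3.19) follow. Step 3.20 is "Imaging for lens centration using Medmont Topographer, over CLs: OD, OS".

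**Visit 4.** Subjects arrive after at least 2 hours of wear. NITBUT (4.10) and COAS (4.12) precede lens removal (4.13) and biomicroscopy (4.14).

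**Analysis.** Section 2.2 lists these measurements as secondary endpoints. Section 14.6 tests each in turn as a predictor of success and does not say which visit's value is used.

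**The concern.** A tear-film test that is meant to be non-invasive comes after dye, and possibly drops, has been put in the eye. The drops are at the examiner's option, so pre-measurement conditions can differ between subjects for reasons unrelated to the trait being measured. Aberrometry and topography are also read from an eye that has just had dye.

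At Visit 3 a second problem is added. The lenses under measurement were put in a few steps earlier, and the protocol sets no minimum time on the eye, although it sets one at Visit 2. Visits 3 and 4 nominally record the same on-lens NITBUT and COAS, but under different conditions.

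The secondary analysis looks for associations between these values and success in a study of about 50 completers, with no power calculation behind that number (Section 14.2). Random error in a predictor weakens its apparent association with the outcome, so a real predictor could be missed.

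**Working it through.** The plan states no variance, reliability or power figure for these measurements, so there is nothing of its own to reproduce. The check is a comparison of step orders, followed by an illustration of size.

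**Step order (Section 7.2 and Table 4)**

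| Measurement | Taken at | Dye earlier in that visit? | Lens on the eye | Taken before dye at any visit? |
|---|---|---|---|---|
| Bare-eye NITBUT | 1.24 | Yes (1.19) | None | No |
| Bare-eye COAS | 1.26 | Yes (1.19) | None | No |
| Bare-eye Medmont reference | 1.27 | Yes (1.19) | None | No |
| On-lens NITBUT | 3.17, 4.10 | Visit 3 yes (3.12); Visit 4 no | New; worn at least 2 h | Yes, Visit 4 |
| On-lens COAS | 3.19, 4.12, 6.12 | Visit 3 yes (3.12); Visits 4 and 6 no | New; worn at least 2 h | Yes, Visits 4 and 6 |
| On-lens Medmont centration | 3.20 | Yes (3.12) | New | No |

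**Settling at Visit 3.** Step 3.8 asks for settling between lens changes, and Table 4 marks insertion and settling at Visit 3 only if the lens is modified. Both concern power modification, which comes before the removal at 3.11. Neither covers the new pair inserted at 3.13.

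**Package insert (Appendix C).** It warns that lenses take up fluorescein and calls for a sterile saline rinse whenever the dye is used. Step 3.12 makes drops or saline optional. These passages need to be reconciled.

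**Size, illustration only.** Let f be the added error variance as a fraction of the between-subject variance, with error unrelated to outcome. Reliability is R = 1/(1+f), and a correlation shrinks by √R:

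- f = 0.25: 1/√1.25 = 0.89 (R = 0.80)
- f = 0.50: 1/√1.50 = 0.82 (R = 0.67)
- f = 1.00: 1/√2.00 = 0.71 (R = 0.50)

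For power, take 50 completers, a single two-sided 5% test and a true difference of d = 0.8 SD between successful and unsuccessful subjects. A two-mean comparison stands in for the planned logistic model:

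power ≈ Φ(d√R · √(n₁n₂/(n₁+n₂)) − 1.96)

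With 25 and 25 subjects and R = 1: 0.8 × √12.5 = 2.83, and Φ(0.87) = 81%. With 37.5 and 12.5 (75% success): 0.8 × √9.375 = 2.45, and Φ(0.49) = 69%.

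| Reliability R | 1.0 | 0.9 | 0.8 | 0.7 | 0.5 |
|---|---|---|---|---|---|
| 50% success | 81% | 77% | 72% | 66% | 52% |
| 75% success | 69% | 64% | 59% | 54% | 41% |

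Across d = 0.6 to 1.0 and success rates of 50%, 60% and 75%, the loss is 2 to 5 points at R = 0.9 and 20 to 29 points at R = 0.5. The values of f, R and d and the success rates are all assumptions.

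**The case against.** **Time passes between steps.** At Visit 1, stereo-acuity, fixation disparity and contrast testing separate the dye from NITBUT. At Visit 3, a questionnaire, stereo-acuity and contrast testing come between insertion and NITBUT, and accommodation testing comes before COAS and centration. This stands: a reader might infer that the Visit 3 lenses are unsettled when measured, but the documents show only that no minimum time is required.

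**Centration compared with Visit 4.** A reader might extend the contrast with Visit 4 to Medmont centration. Visit 4 has no Medmont imaging; it only grades centration in the fit assessment. The Visit 1 Medmont image is a bare-eye reference, not a centration measurement.

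**Same-day lens wear at Visit 1.** A reader might infer a bias between habitual lens wearers and others. The Synopsis and the Visit 1 instructions have wearers arrive in lenses, but the opening of Section 7.2 has all subjects attend screening in spectacles. The text contradicts itself, so this bias cannot be asserted.

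**Copying the Visit 4 order at Visit 3.** This looks like the obvious remedy. However, subjects with unchanged power would then be measured after at least 2 hours of wear, and those just re-powered after about 10 minutes. Step 3.8 triggers modification when vision or over-refraction is unacceptable, which is plausibly related to success. The current order, with everyone on new lenses, avoids that imbalance.

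**Redaction and sequence.** Appendix Q and the COAS and biomicroscopy procedures are blacked out and could contain interval or settling instructions. The protocol also never says that numbered steps must be done in order. Both points are fair, but neither changes the visible order, and step 3.13 refers back to step 3.11, so sequence is intended there.

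**Partial mitigation.** On-lens NITBUT and COAS do have cleaner values at Visit 4. That helps only if the analysis uses them, and Section 14.6 does not say so.

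**Conclusion.** The point holds as a low-severity improvement. In the visible text, dye precedes these measurements at two visits with no stated interval, and at Visit 3 new lenses are measured with no required settling time. Bare-eye NITBUT, bare-eye COAS and on-lens centration have no cleaner repeat. On-lens NITBUT and COAS do, at Visit 4.

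The documents support avoidable error as a possibility, not a measured effect. The shrinkage factors of 0.89 to 0.71 and the power losses rest on assumed error variances, and on error unrelated to outcome. Nothing in the documents shows how far dye shifts aberrometry or topography. The conclusion also assumes that the redacted procedures do not already set an interval or settling time, and that staff follow the numbered order.

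**What to change.** 1. **Visit 1 measurements.** Move 1.24, 1.26 and 1.27 to Visit 2, between 2.7 and 2.8. Eligibility is then known, no lenses have been worn that day, and no dye has yet been instilled at that visit.
2. **Arrival at Visit 1.** Reconcile the opening of Section 7.2 (spectacles) with the Synopsis and the Visit 1 instructions (habitual lenses).
3. **Visit 3.** Keep every subject on newly inserted lenses, so that modified and unmodified subjects stay comparable, and apply the step 2.12 settling time after 3.13 and before 3.15 to 3.20. The centration image would still follow dye, but with a common minimum time on the eye.
4. **Section 14.6.** Name the Visit 4 values as the on-lens NITBUT and COAS predictors. The analysis population has completed all visits (Section 14.3), so this choice does not itself exclude anyone.

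**Cost.** Visit 2, already estimated at 3.5 hours, lengthens by about what Visit 1 saves. Visit 3 gains about 10 minutes. Table 4, the Synopsis and the eCRFs need matching edits, and the amendment goes to the ethics committee under Section 18.3. No new procedure or equipment is needed.

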7.3. Unscheduled Visits

If, during the investigation, a participant requires an unscheduled visit to the clinical site, the following information will be collected at a minimum:

- Chief complaint prompting the visit. If the reason is an adverse event, the applicable eCRF for the adverse event must be completed and participant record completed as appropriate
- Date and time of the visit and all procedures completed at the unscheduled visit
- Review of adverse event and concomitant medications
- Documentation of any test article dispensed or collected from the participant, if applicable
- Slit lamp findings (using the Slit Lamp Classification Scale)

If the Investigator withdraws a participant from the study, the final study visit case report forms must be completed indicating the reason(s) why the participant was withdrawn. The participant record must be completed documenting the date and primary reason for withdrawal and the study CRA notified.

Any ocular and non-ocular Adverse Events that are ongoing at the time of the study visit will be followed by the Investigator, within licensure, until they have resolved, returned to pre-treatment status, stabilized, or been satisfactorily explained. If further treatment i.e., beyond licensure is required, the participant will be referred to the appropriate health care provider.

The following information may be collected during an unscheduled visit as required.

Unscheduled Visit			
Step	Procedure	Details	
U.1	Chief Complaints	Record the participant's chief complaints for reasons for the unscheduled visit.	
U.2	Adverse Events and Concomitant Medications Review	Review any changes to the participant's medical history or concomitant medications from the previous study visit. Record any changes, and any adverse events.	

Unscheduled Visit			
Step	Procedure	Details	
U.3	Subject Reported Ocular Symptoms	If the participant reports ocular symptoms with their lenses, they will be recorded in the Subject Reported Ocular Symptoms eCRF	
U.4	Entrance logMAR HCVA	Record the entrance distance visual acuity (OD, OS and OU) to the nearest letter.	
U.5	Subjective Spherocylindrical Refraction	Perform bare-eye subjective spherocylindrical refraction with a phoropter (adopt the maximum plus to maximum visual acuity (MPMVA) approach and use the duo-chrome test for binocular balancing) and record the best corrected distance visual acuity to the nearest letter (OD, OS, and OU).	
U.6	Biomicroscopy	Non-dilated Slit Lamp Biomicroscopy will be performed. If the clearance of the fluorescein needs to be expedited, preservative-free rewetting drops or saline may be instilled.	
U.7	Lens Fit Assessment	Evaluate and grade lens centration, primary gaze movement, upgaze movement and tightness (push-up test). The participant should not proceed to wear the lenses if any of the following is observed: 
 • presence of limbal exposure (appearance of clear cornea) in any gaze • presence of edge lift • presence of unacceptable movement (excessive or insufficient) in all three movement categories (primary gaze, upgaze, and push-up). 
If either lens is deemed unacceptable, the participant will be discontinued from the study. Remove the lenses, perform a slit-lamp evaluation, and complete the Final Evaluation form.
	
U.8	Exit logMAR HCVA	Record the participant's exit distance visual acuity (OD, OS, and OU) to the nearest letter.	
U.9	Dispensing Criteria	For the participant to continue in the study, they must meet all three of the following criteria: 
 • Distance Binocular Visual acuity is 0.18 or better • The lens fit is acceptable OD and OS • Investigator approval. 	

Unscheduled Visit			
Step	Procedure	Details	
		If the Investigator does not approve the dispensing of the study lens, then the study is terminated for that participant.	
U.10	Dispensing of Lenses / Solutions (if applicable)	Subjects will be dispensed enough lenses & solutions to last them until their next visit. Subjects are permitted to use Refresh Plus® their habitual CL rewetting drops with the study lenses. Use of any other artificial tears/lubricating eye drops is not permitted with study CLs.	
U.11	Patient Instructions (if applicable)	
Instruct the Subject the following:
 
 • The lenses will be worn on a daily wear daily disposable basis. • Only enough lenses will be dispensed to the subject to wear for the required number of days until their follow-up visit. No additional lenses will be dispensed. • Instruct the subject to bring back all unworn study lenses. • If determined necessary by the Investigator Refresh Plus® sterile non-preserved rewetting drops may be dispensed to be used as needed for dryness. • Subjects will be instructed to wear lenses for a minimum of 6 hours a day every day during the study. • Subjects will be instructed to wear their glasses (if applicable) when not wearing the study lenses. • A patient instruction booklet will be provided. 
Note: In the event a lens is lost or damaged, the subject will return to the investigator site for replacement. As much as reasonably possible, a damaged lens should be returned to the investigational site and then returned to the Sponsor. If lens damage is present, complete the Product Quality Complaint
	

Unscheduled Visit			
Step	Procedure	Details	
		Form. The lens will be stored in labeled vial with sterile saline and returned to the Sponsor.	
U.12	Wear Schedule for Neophytes / Lapsed Wearers	
The test lenses will be worn on a daily wear, daily disposable basis.
 
Note: Instruct the Neophytes / Lapsed wearer subjects to follow this wear schedule for wearing the study lenses: Dispensing day: 6 hours of wear Day 1: 6-8 hours of wear Day 2: 6-10 hours of wear Day 3: 6-12 hours of wear Day 4 and subsequent days: 6 to all waking hours of wear
 
Note: For this protocol a day of wear is considered to be a minimum of 6 hours. When not wearing the study lenses the participant should be instructed to only wear their glasses (If applicable). For the follow-up visit instruct the participant they must have worn the lenses for at least 2 hours.
	

